5	AML (approximately 68 subjects [24 per cohort in Part 5A, 20 in Part 5B])	Part 5A: AMG 176 in combination with azacitidine Cohorts 1 and 2: OBD Selection (QW or BIW). Part 5B: Conventional AML Dosing Schedule (5 consecutive days)	
Part 5 will begin after the completion of Part 4.
 
Part 5A:
 
Two cohorts will be enrolled to determine the combination RP2D/OBD on either a QW or BIW dosing schedule.Simon's two-stage minimax design (Simon, 1989) will be used in each cohort of Part 5A for conducting the trial.Enrollment will be restricted to subjects with persisting or recurring AML ≤ 2 prior lines of therapy. 
Part 5B (The enrollment of Part 5B will start after Part 5A is complete):
 
Two regimens will be tested, both continuing to utilize a 28-day cycle.All subjects will receive 7 days of azacitidine IV or SC daily at 75 mg/m^2 on Days 1 - 5, 8 - 9 of each 28-day cycle.Regimen 1 will administer AMG 176 at 240 mg/m^2 QD for 3 days + 4 days off followed by BIW dosing on weeks 2 and 3.Regimen 2 will administer AMG 176 at 240 mg/m^2 QD for 5 consecutive days, and then BIW on week 2 (no administration on weeks 3 and 4). Regimen 2 will only enroll if no safety issues arise after 6 subjects have enrolled in Regimen 1.Doses other than the stated 240 mg/m^2 based on emerging data.

AML = acute myeloid leukemia; BIW = twice weekly; DLRT = dose-level review team; IV = intravenous; MM = multiple myeloma; MTD = maximum tolerated dose; mTPI = modified toxicity probability interval; PD = pharmacodynamics; PK = pharmacokinetics; QD = once daily; QW = once weekly; RP2D = recommended phase 2 dose; SC = subcutaneous; US = United States

Note: Part 2 was designed to be a combination treatment for MM in a previous amendment. It was removed due to a change in AMG 176 clinical development.

Number of Subjects

Subjects with relapsed or refractory MM and subjects with relapsed or refractory AML are eligible for this study (see Section 5). It is anticipated that **approximately 219 subjects** will be enrolled in the different parts of this study.

CLOSED TO ENROLLMENT: Multiple myeloma Part 1a enrolled 36 subjects for dose escalation. Multiple myeloma Part 1b enrolled 12 subjects for dose escalation. Acute myeloid leukemia Part 3a enrolled 17 subjects for dose escalation. Part 3b enrolled 11 subjects. Acute myeloid leukemia Part 3c enrolled 4 subjects in Japan.

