^d AMG 176 will be administered in monthly cycles of treatment. Each cycle AMG 176 BIW is defined as an IV infusion once daily for two consecutive days followed by a 5-day break and repeated each week for 3 consecutive weeks followed by one week with no treatment.

[figure not shown]
^e Azacitidine will be administered at a dose of 75 mg/m² either IV or SC, as recommended in the prescribing information, daily for the first 7 days of a 28-day cycle.

^f AMG 176 QW and BIW cohorts may be conducted in parallel.

^g A safety follow-up visit will take place 30 days (+3 days) after the last dose of AMG 176.

^h Long-term follow-up assessments will occur every 3 months (± 14 days) after end of treatment (EOT) for 1 year.

Figure 1-10. Study Design and Treatment Schema – Acute Myeloid Leukemia Part 5B AMG 176 Conventional Dosing

BIW = twice weekly; DLRT = dose-level review team; IV = intravenous

^a Approximately 20 subjects will be enrolled for Part 5B.

^b AMG 176 is administered as an IV infusion on a 28-day cycle for 3 consecutive days the first week, and BIW on weeks 2 and 3 each cycle of each 28-day cycle in the first 6 subjects (Regimen 1). If this schedule is deemed safe by the DLRT, the next 6 subjects will receive dosing on 5 consecutive days the first week, and BIW in week 2 for each 28-day cycle (Regimen 2). If Regimen 2 is deemed safe by the DLRT, then further enrollment to Part 5B may proceed at either Regimen 1 or Regimen 2, as determined by the study team.

^c A safety follow-up visit will take place 30 days (+3 days) after the last dose of AMG 176.

^d Long-term follow-up assessments will occur every 3 months (\pm 14 days) after end of treatment (EOT) for 1 year.

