4	AML	AMG 176 in combination with azacitidine	Cohorts 1-4 ^c : AMG 176 QW IV (60, 120, 180, and 240 mg/m ²) in combination with azacitidine Cohort 5a ^c : AMG 176 BIW IV (120 mg/m ²) in combination with azacitidine Cohort 5b ^c : AMG 176 BIW IV (240 mg/m ²) in combination with azacitidine	Approximately 60 subjects	An mTPI design will be used to define the combination RP2D. Safety, tolerability, PK, and PD of AMG 176 in combination with azacitidine will also be established. Part 4 enrollment will begin once 120 mg/m ² of Part 3b is cleared as safe and tolerable by the DLRT. Azacitidine will be administered at a dose of 75 mg/m ² either IV or SC, as recommended in the prescribing information, daily for the first 7 days of a 28-day cycle.
5A	AML	AMG 176 (QW or BIW) in combination with azacitidine	Cohort 1-2: RP2D in combination with azacitidine	Approximately 48 subjects ^d	Part 5 (dose expansion) will begin once the combination RP2D has been determined from Part 4. Simon's two-stage minimax design (Simon, 1989) will be used for conducting trial in each cohort of Part 5A. The null hypothesis is that the true response rate (CR or CRI) is 0.1 and the alternative hypothesis is that the true response rate (CR or CRI) is 0.32. The design controls the two-sided type I error rate at 0.05 and yields the power of 0.8. The total estimated sample size is 48, with 24 subjects in each cohort.

Page 2 of 3

Footnotes defined on last page of the table

Table 4-1. Overview of Study Design (continued)

Part	Indication	Cohort/Treatment Group	AMG 176 Dose Levels ^{a, b}	Number of Subjects	Design
OPEN TO ENROLLMENT					
5B	AML	AMG 176 conventional dosing	AMG 176 on 3 consecutive days the first week, and BIW on weeks 2 and 3 each cycle (Regimen 1) and on 5 consecutive days the first week, and BIW on week 2 for each cycle (Regimen 2)	Approximately 20 subjects ^{d, e}	Two regimens will be tested, both utilizing a 28-day cycle. Regimen 1 consists of receiving AMG 176 at 240 mg/m ² QD for 3 days + 4 days off followed by BIW dosing on weeks 2 and 3. If this schedule is deemed safe by the DLRT after 6 subjects have enrolled on Regimen 1, Regimen 2 subjects will receive AMG 176 at 240 mg/m ² QD for 5 consecutive days, and then BIW on week 2. The enrollment of Part 5B will start after Part 5A is complete.

Page 3 of 3

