
For AML Part 3b and Part 4, each dose cohort will initially enroll 3-4 subjects and up to 10 subjects per cohort may be enrolled. After reviewing all available safety and tolerability data, dose level decisions (eg, escalation/de-escalation/expansion) will be made by the DLRT using a modified Toxicity Probability Interval (mTPI) model (Ji et al, 2010) based on all subjects that have been enrolled at current dose. Dose escalation is considered to be complete if one of the following rules is met:

- The highest planned dose level is evaluated, MTD/MTCD has not been defined and no DLTs occur at any dose level. In this case the maximum administrated dose (MAD) may be used for phase 2.
- An MTD/MTCD is identified.

Guidelines for dose level decisions can be found in [Table 4-2](#). Details regarding the mTPI model and dose finding are described in Section [11.16](#). Please note one exception to the guidelines provided in [Table 4-2](#), a single grade 3 treatment-related troponin elevation will result in dose de-escalation regardless of number of subjects treated at current dose.

Table 4-2. Guidelines for Dose-level Decisions for Part 3b and Part 4

No. of DLT-evaluable ^a subjects treated at current dose	Number of DLTs		
	Escalate	Stay at current dose	De-escalate ^b
3	0	1	≥ 2
6	0-1	-	≥ 2
9	0-1	2	≥ 3
10 ^c	0-1	2-3	≥ 4

DLT = dose-limiting toxicity

^a A subject is considered DLT-evaluable if he/she experienced a DLT during the DLT evaluation period or if he/she received 75% of the planned doses of AMG 176 and completed the DLT evaluation period.

^b De-escalate guideline applies only when current dose level and enrollment is allowed to a lower dose level.

^c The maximum number of evaluable subjects at one dose level is 10.

The MTD/MTCD is defined as the highest dose with a probability of DLT lower than or close to a targeted toxicity probability of 0.2.

For the first dose level and at each new higher dose level, the first enrolled subject will be treated, and then after a period of 72 hours, subsequent subjects will be treated, provided that there are no significant toxicities relating to the treatment of the first subject.

In addition to safety, efficacy of complete remission per ELN in Part 4 will be evaluated. At MTCD or optimal biological dose (OBD), 1 complete remission out of 6 subjects, or 2 complete remissions out of 10 subjects are expected.

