Upon completion of Part 4, enrollment will commence in Part 5A to confirm the safety and tolerability of the two selected doses along with the dosing schedule (QW or BIW) and to further evaluate the preliminary efficacy of AMG 176 in combination with azacitidine. In Part 5A, approximately 48 subjects will be enrolled, with 24 subjects randomized to the cohort of AMG 176 120 mg/m² in combination with azacitidine and 24 subjects randomized to the cohort of AMG 176 240 mg/m² in combination with azacitidine, where the same dosing schedule (QW or BIW) will be used for both cohorts. Simon's two-stage minimax design (Simon, 1989) will be used for conducting the trial in each cohort of Part 5A. Details about Simon's two-stage minimax design are provided in Section 9.4.1.1.

In Part 5B, 20 subjects will be enrolled to test 2 regimens. The enrollment of Part 5B will start after Part 5A is complete. Regimen 1 consists of administering AMG 176 at 240 mg/m² QD for 3 days + 4 days off followed by BIW dosing on weeks 2 and 3. If this schedule is deemed safe by the DLRT after 6 subjects have enrolled on Regimen 1 cohort, the next 6 subjects in Regimen 2 cohort will receive AMG 176 at 240 mg/m² QD for 5 consecutive days, and then BIW on week 2. Safety data will be monitored continually.

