If a subject develops a reaction during or after the AMG 176 infusion, immediate treatment should be initiated according to best clinical practice. Increase monitoring of vital signs as medically indicated until the subject is deemed medically stable in the opinion of the investigator. All medication and symptoms should be documented in the eCRF.

Intra-subject Dose Escalation

For each part, DLTs will be assessed during the DLT evaluation period. Subjects who complete the DLT-observation period without experiencing a DLT may proceed to a higher dose level or different dosing schedule cohort once the target cohort has been deemed safe by the DLRT and after consultation with the sponsor. Dose-limiting toxicities experienced by subjects who proceeded to a higher dose or different schedule will not be considered for dose level decisions. However, the DLRT will take this information into account to inform dose escalation recommendations.

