6.2.1.1 Dose-Limiting Toxicity Evaluation Period

The minimum DLT evaluation period is defined as 4 weeks of treatment in cycle 1.

The DLT evaluation period may also be extended to assess events starting within the evaluation period in case the DLT definition is time dependent (neutropenia or thrombocytopenia, see below).

Subjects are considered DLT-evaluable if they experienced a DLT during the DLT evaluation period or if they received 75% of the planned doses of AMG 176 (and 100% of the planned doses of azacitidine in Part 4) and completed the DLT evaluation period.

Subjects who did not complete 75% of the planned doses of AMG 176 (and 100% of the planned doses of azacitidine in Part 4) or discontinue from the study prior to completing the DLT evaluation period for reasons other than a DLT will be considered non DLT-evaluable for dose escalation decisions and MTD/MTCD determination and will be replaced by an additional subject at that same dose level. Subjects who receive supportive care during the DLT evaluation period that confounds the evaluation of DLTs (not including supportive care described in Section 6.2.1.2 as part of the DLT definition) may be considered non-evaluable for dose escalation decisions and MTD determination and replaced at the discretion of the Medical Monitor.

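### Part 5B lets the DLRT open the 5-consecutive-day Regimen 2 once six subjects have enrolled on Regimen 1, with no minimum follow-up required

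*Protocol*

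**What the plan says.** **Opening Regimen 2.** Protocol 4.1.1 makes it conditional: "If this schedule is deemed safe by the DLRT after 6 subjects have enrolled on Regimen 1 cohort". Table 4-1 has the same condition, "deemed safe by the DLRT after 6 subjects have enrolled on Regimen 1". The synopsis (1.1) says "Regimen 2 will only enroll if no safety issues arise after 6 subjects have enrolled in Regimen 1", and the SAP design table (3.1) repeats the synopsis. Table 1-1, Figure 1-10 footnote b, Table 1-9 and Section 4.3 speak only of six subjects followed by a DLRT finding of safety.

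**After Regimen 2.** Figure 1-10 footnote b says "If Regimen 2 is deemed safe by the DLRT, then further enrollment to Part 5B may proceed at either Regimen 1 or Regimen 2". Table 4-1 footnote e agrees. Section 4.3 instead sends the remaining subjects to Regimen 2. None of the three states a follow-up requirement.

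**The DLT window.** Section 6.2.1.1 says "The minimum DLT evaluation period is defined as 4 weeks of treatment in cycle 1", and allows an extension when the DLT definition is time-dependent (neutropenia or thrombocytopenia). To be evaluable without a DLT, a subject needs 75% of the AMG 176 doses, a completed window and "100% of the planned doses of azacitidine in Part 4".

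**Other parts of the plan.** Table 4-2, which covers Parts 3b and 4, counts only DLT-evaluable subjects; without a DLT, a subject counts "if he/she received 75% of the planned doses of AMG 176 and completed the DLT evaluation period". For individuals, Section 6.1.1 says "Subjects who complete the DLT-observation period without experiencing a DLT may proceed to a higher dose level or different dosing schedule cohort".

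**The concern.** Part 5B exists to explore the safety of consecutive-day dosing (Section 4.3.2). The one decision that moves new subjects from three to five consecutive days is tied to a count of enrolled subjects, not to observed subjects or completed follow-up. Enrollment is also the earliest status a subject can have: under Section 5.3 a subject is enrolled once the investigator decides that eligibility is met, which can precede dosing.

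If the DLRT decided early, some Regimen 1 subjects might have had no dose at the 240 mg/m² target, because days 1 and 2 of cycle 1 are ramp-up days (6.1.4.1). The AML hematologic DLT in Table 6-1 needs grade 4 neutropenia or thrombocytopenia lasting at least 42 days from the start of the cycle, so it cannot yet be seen in recently enrolled subjects. The same applies to the second decision, which governs about 20 − 6 − 6 = 8 further subjects.

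**Working it through.** **1. Is a follow-up requirement stated anywhere?**
- *The Part 5B texts:* four places use enrolled (Protocol 1.1, Table 4-1, 4.1.1; SAP 3.1) and four give only six subjects and a DLRT finding. None gives a follow-up time or an evaluable count.
- *Sections 4.1.1 and 6.1.1* say that DLTs are assessed in each part during the evaluation period. That says when DLTs are assessed, not when Regimen 2 may open.
- *Sections 9.4.1.1 and 11.3* have the DLRT review all available data, including data after the DLT window. Availability sets no minimum.
- *Table 4-2* is limited to Parts 3b and 4, and Table 9-1 has no Part 5B row.

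**2. Dose difference between the regimens.** Inputs: ramp-up dose 120 mg/m² (6.1.1), given on days 1 and 2 of cycle 1 in Part 5B, with target 240 mg/m² from day 3 (6.1.4.1). Dosing days are 1, 2, 3, 8, 9, 15, 16 for Regimen 1 and 1–5, 8, 9 for Regimen 2.

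| | Regimen 1 | Regimen 2 | Ratio |
|---|---|---|---|
| Cycle 1, week 1 | 2×120 + 1×240 = 480 | 2×120 + 3×240 = 960 | 2.00 |
| Cycle 1, total | 2×120 + 5×240 = 1440 | 2×120 + 5×240 = 1440 | 1.00 |
| Later cycles, week 1 | 3×240 = 720 | 5×240 = 1200 | 1.67 |
| Later cycles, total | 7×240 = 1680 | 7×240 = 1680 | 1.00 |

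All doses are in mg/m². In cycle 1 the regimens do not differ until day 4.

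**3. What six subjects can show.** Protocol 9.2 states a 47% to 91% chance of at least one DLT with six subjects at true rates of 10% to 33%. The formula is 1 − (1 − p)ⁿ.
- n = 6: 1 − 0.90⁶ = 46.9%; 1 − 0.67⁶ = 91.0%. The stated figure is reproduced.
- n = 3: 1 − 0.90³ = 27.1%; 1 − 0.67³ = 69.9%, matching the protocol's own 27% to 70%.
- n = 2: 19.0% and 55.1%.

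The six-subject figure holds only if all six are followed through the window. The smaller figures count completed subjects alone; a partly followed subject can still have a DLT.

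**4. Illustration of follow-up.** Accrual is not stated. Assume a constant gap g between enrollments, dosing on the day of enrollment, and a decision on the day the sixth subject enrolls. Subject k then has g × (6 − k) days of follow-up. For g = 7 these are 35, 28, 21, 14, 7 and 0 days, and the Regimen 1 doses already given are 7, 7, 7, 5, 3 and 0.

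| Gap (days) | With ≥ 28 days | With all 7 cycle 1 doses | With ≥ 42 days |
|---|---|---|---|
| 3.5 | 0 of 6 | 1 of 6 | 0 of 6 |
| 7 | 2 of 6 | 3 of 6 | 0 of 6 |
| 14 | 4 of 6 | 4 of 6 | 3 of 6 |
| 28 | 5 of 6 | 5 of 6 | 4 of 6 |

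These counts mark the early end of what the wording allows. They do not forecast what the DLRT would do.

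**The case against.** **Enrolled may describe cohort size, not a decision date.** Section 4.1.1 also bases Part 3b and 4 decisions on subjects enrolled at the current dose, yet Table 4-2 counts evaluable subjects. This reading is fair, and four of the Part 5B texts fit it. It does not close the gap: in Parts 3b and 4 Table 4-2 supplies the follow-up rule, and in Part 5B nothing does.

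**The DLRT is a real safeguard.** It reviews queried data, needs a quorum of more than half the participating investigators, may delay dosing or repeat a cohort, and enrollment can be stopped at any time (6.2.1, 11.3). Safety is monitored continually, and Part 5B follows Part 5A. This stands and makes a decision on the very day of the sixth enrollment unlikely. It leaves waiting to discretion.

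**The omission may be deliberate.** Within Parts 4 and 5 the objectives make DLT incidence an endpoint for Part 4 only, so the azacitidine condition naming Part 4 is consistent with them and need not be an oversight. Agreed. But a safety decision can use the DLT window without making DLT incidence an endpoint.

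**The exposure step is modest.** Cycle totals are equal. For 240 mg/m² on five consecutive days versus BIW, modelled median Cmax rises 1.1-fold and AUC over 168 hours 1.9-fold (4.3.2). This limits the consequence. It is modelling, however, and 4.3.2 cites no clinical data on consecutive dosing for three or five days.

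**Conclusion.** The point holds as a gap in what the plan requires. The DLRT may open Regimen 2, and later allow further Part 5B enrollment, without the preceding six subjects having completed cycle 1. The change at issue is week 1 dose concentration, 2.00-fold in cycle 1 and 1.67-fold afterwards, with equal cycle totals.

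A reader might infer more, and the documents do not support it:
- *That the sixth enrollment opens Regimen 2 automatically, or that an early decision is prescribed.* A DLRT finding of safety is always needed.
- *That Regimen 2 doubles the drug given.* It doubles cycle 1 week 1 only.
- *That subjects were in fact moved too soon.* SAP Section 10 reports early termination, and nothing shows that Part 5B enrolled anyone.

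The textual finding and the dose sums rest on the documents. The follow-up counts rest on assumed accrual, same-day dosing and an immediate decision, and are illustrative only. The existing safeguards make this a worthwhile protection for subjects rather than a fundamental flaw.

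**What to change.** In Protocol 1.1, Table 4-1, 4.1.1 and SAP 3.1, replace the enrollment condition with this: *the DLRT decides after six DLT-evaluable Regimen 1 subjects have completed the cycle 1 DLT evaluation period of Section 6.2.1.1, including its extension for an ongoing neutropenia or thrombocytopenia, or have had a DLT.* Apply the same condition to the Regimen 2 decision before further Part 5B enrollment (Figure 1-10 footnote b, Table 4-1 footnote e, Section 4.3).

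Consequential edits:
- **Protocol 4.2.1** limits replacement of non-evaluable subjects to dose escalation and, outside Part 3d, allows no other replacement. Extend it to Part 5B.
- **Protocol 6.2.1.1 and SAP 6.7.2** name Part 4 only in the azacitidine condition. Extend it to Part 5B for these decisions only.

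The DLT criteria and window stay as they are, the judgment of safety stays with the DLRT, and DLT incidence need not become a Part 5 endpoint.

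The cost is a pause of up to about 28 days after the sixth subject starts, at each of the two decisions. It is longer if a cytopenia is being followed or a subject is replaced, and a few replacement subjects may be needed.

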4.1.2 AMG 176 Tolerability in Subjects with AML in Japan (Part 3c)
AML subjects will be confirmed according to a standard 3+3 design without dose escalation. Three subjects with relapsed or refractory AML will be enrolled into Part 3c and treated with AMG 176 using the QW dosing schedule (see Part 1b for description). Three additional subjects will be enrolled if 1 of initial 3 subjects experience a DLT. A dose with > 33% subjects experiencing a DLT is defined as not tolerable. The tolerable dose of investigational drug is defined as a dose at which fewer than one-third of subjects experience a DLT. If 2 or more of 6 subjects experience a DLT, appropriate action will be discussed by DLRT.

4.1.3 Drug-drug interaction Assessments with Itraconazole in the United States (Part 3d)

A separate cohort of about 11 subjects with AML will be enrolled for this DDI assessment using a fixed sequence design ([Figure 1-7](#)), where AMG 176 will be

co-administered with itraconazole during week 1 followed by dosing of AMG 176 alone in subsequent weeks. Since subjects are hospitalized during the first week of AMG 176 dosing, itraconazole administration will be limited to the first week to ensure proper monitoring and oversight of subjects in the event of increased exposure to AMG 176. A 7-day sentinel dosing will be utilized between the first and second subject enrolled in this cohort. All safety data available will be evaluated in the first subject prior to enrolling all subsequent subjects.

Subjects will receive:

- Oral itraconazole capsules (200 mg) QD starting at 8 am on day -3 through day 4 (total of 7 days) to achieve adequate CYP3A4 inhibition prior to, and following, AMG 176 administration.
- Intravenous AMG 176 (60 mg/m²) on day 1 at approximately the same time as itraconazole dosing (± 5 minutes).

Serial PK sampling will be conducted at specified time points after the AMG 176 dose on day 1 to characterize the plasma concentrations of AMG 176 when given in combination with itraconazole. Subjects will receive AMG 176 (60 mg/m²) alone on day 8 and day 15. Serial PK sampling will be conducted at specified time points after the AMG 176 dose on day 15 to characterize the plasma concentrations of AMG 176 without itraconazole. AMG 176 pharmacokinetics will be compared from day 1 (with itraconazole) relative to day 15 (without itraconazole). After day 15, subjects will be eligible to receive the highest cleared monotherapy or combination therapy dose if deemed safe by the investigator and Amgen medical monitor.

